10.2. Health Outcome Measures

The health outcome measures listed below will be administered. Country-specific translations of each measure will be available in this study. Items being measured using a paper diary should be completed at the end of the patient's day (typically their bedtime).

- Morning Joint Stiffness Severity Numeric Rating Scale (NRS): The Morning Joint Stiffness NRS is a patient-administered, single-item, 11-point horizontal scale anchored at 0 and 10, with 0 representing “no joint stiffness” and 10 representing “joint stiffness as bad as you can imagine.” Patients rate their morning joint stiffness each day (using a paper diary) by selecting the one number that describes their overall level of joint stiffness at the time they woke up.
- Duration of morning joint stiffness:
 - Patient diary: The duration of morning joint stiffness is a patient-administered item that allows for the patients to enter the length of time in hours and minutes that their morning joint stiffness lasted each day.
 - Electronic PRO (tablet): The duration of morning joint stiffness is a patient-administered item that allows for the patients to enter the length of time in minutes (using 15-minute increments) that their morning joint stiffness lasted on the day prior to that visit (using an electronic patient-reported outcomes [ePRO] tablet).
- Recurrence of joint stiffness: The recurrence of joint stiffness throughout the day is a patient-administered single-item question assessed each day (using a paper diary) that asks “Did you have any joint stiffness throughout today, other than when you woke up?” (Yes/No)
- Tiredness Severity Numeric Rating Scale (Worst Tiredness NRS):
 - Patient diary: The Worst Tiredness NRS is a patient-administered, single-item, 11-point horizontal scale anchored at 0 and 10, with 0 representing “no tiredness” and 10 representing “as bad as you can imagine.” Patients rate their tiredness each day (using a paper diary) by selecting the one number that describes their worst level of tiredness.

- Electronic PRO (tablet): The Worst Tiredness NRS is a patient-administered, single-item, 11-point horizontal scale anchored at 0 and 10, with 0 representing “no tiredness” and 10 representing “as bad as you can imagine.” Patients rate their tiredness by selecting the one number that describes their worst level of tiredness during the past 24 hours.
- Severity of joint pain Numeric Rating Scale (Worst Joint Pain NRS):

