- Electrocardiograms will be performed locally and will be locally (machine) read.

- e If the PPD test is positive and the patient has no medical history or chest x-ray findings consistent with active TB, the patient may have a QuantiFERON TB Gold or T-SPOT.TB test (if available). If the QuantiFERON-TB Gold or T-SPOT.TB test results are not negative, the patient will be considered to have latent TB. If the QuantiFERON-TB Gold or T-SPOT.TB test is available and in the judgment of the investigator, preferred as an alternative to the PPD skin test for the evaluation of TB infection, it may be used instead of the PPD TB test. If the QuantiFERON-TB Gold or T-SPOT.TB test is positive, the patient will be considered to have latent TB. If the test is not negative, the test may be repeated once within 2 approximately weeks of the initial value. If the repeat test results are again not negative, the patient will be considered to have latent TB.
- f A chest x-ray will be taken locally at screening unless one has been obtained within the past 6 months (provided the x-ray and/or report are available for review).
- g At Visit 2, the patient will take his/her oral investigational product at the clinic under the supervision of study staff.
- h At Visits 3, 4, and 8, patients should bring their investigational product with them to the study visit, but no tablet counts need to be performed.
- i All the radiographic images of the hands and feet will be submitted to the central reader for reviewing. At screening, radiographic images of the hands and feet acquired within 4 weeks prior to study entry may be submitted to the central reader to confirm eligibility. If a patient undergoes rescreening, radiographic images acquired as part of initial screening and within 10 weeks of randomization may be used.
- j X-rays will only be taken at early termination if the most recent x-ray was more than 12 weeks earlier.
- k Morning joint stiffness, Worst Tiredness, and Worst Joint Pain assessments will be collected using paper patient diary through Week 12 to assess duration, severity of morning joint stiffness, recurrence of stiffness during the day, worst tiredness and worst joint pain.
- l Morning joint stiffness duration, Worst Tiredness, and Worst Joint Pain assessments will be collected using an electronic patient-reported outcomes [ePRO] tablet at each visit.

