- All baricitinib exposures across all periods, regardless of initial treatment, use of rescue treatment, or protocol-defined switch of assigned treatment, ie, pooled across all cohorts who received baricitinib prior to entering Part C.

6.1.1. *Definition of Baseline and Postbaseline Measures*

The baseline period is defined as Visit 1 through pre-dose (expected at Visit 2). The treatment period for the blinded placebo and active study drug period (Part A) starts after the first study drug administration at Visit 2 (Week 0) and ends on the date of Visit 11 (Week 24) or an early discontinuation visit before Visit 11 (Week 24). The treatment period for the unblinded active study drug period (Part B) starts after the first study drug administration at Visit 11 (Week 24) and ends on the date of Visit 15 (Week 52) or an early discontinuation visit in the treatment

period. The post-treatment follow-up period (Part C) starts after the date of Visit 15 (Week 52) or an early discontinuation visit and lasts until the follow-up visit, which occurs approximately 28 days following the last dose of the study drug, for patients who do not enter long-term extension Study JADY.

The baseline value for the efficacy analyses of the treatment period, including post-rescue analyses, is defined as the last non-missing measurement on or prior to the date of first study drug administration (expected at Week 0, Visit 2), regardless of rescue status. If the Physician's Global Assessment of Disease Activity score is recorded ≤ 5 days after the date of first study drug administration, it will still be used as the baseline value. Postbaseline measurements are collected after study drug administration (expected at Week 0, Visit 2) through Week 52 (Visit 15) or early discontinuation visit.

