6.13. Health Outcomes Analyses

6.13.1. Diary Data

6.13.1.1. Data Handling and Missing Data Imputation

The paper diary data (duration of morning joint stiffness, severity of morning joint stiffness, worst joint pain, worst tiredness, and recurrence of morning joint stiffness during the day) will be assessed daily from Week 0 (Visit 2) to Week 12 (Visit 7). The primary analysis is based on the scores collected in the 7 days prior to the Week 12 visit date. Similar analysis will be done for 7 days prior to each scheduled visit (Week 1, Week 2, Week 4, and Week 8) using the primary analysis method. The supportive analysis is based on daily data modeled by weekly means. The weeks are defined as follows: Day 1 on diary, Days 2-8 (Week 1), Days 9-15 (Week 2), and so on up to Days 79-85 (Week 12).

For the primary analysis, the average of the scores collected in the 7 days prior to Week 12 will be used. If there are fewer than 4 nonmissing scores, the 7-day window will be shifted back in time (toward baseline) 1 day at a time until there are 4 nonmissing scores available in the 7-day window. Then the average of the 4 scores will be used in the Week 12 analysis. This will be repeated for each scheduled visit (week 1, week 2, week 4, week 8) prior to week 12.

For patients who discontinue the study or permanently discontinue the study treatment, the scores collected in the last 7 days prior to discontinuation will be used in the analysis. If a patient undergoes a temporary interruption of study drug at the time of study database lock, this patient will be treated as having permanently discontinued from study drug in the missing data imputation. If there are fewer than 4 nonmissing scores, a similar approach will be used to find 4 nonmissing scores in a 7-day window and the average score will be used in the Week 12 analysis. Patients who do not have at least 4 scores in any postbaseline 7-day window up to Week 12 will have their Day 1 score carried forward to the endpoint for analysis. If the Day 1 value cannot be obtained, the first available postbaseline score will be used to impute the Day 1 score so that the patient can be included in the analysis.

For the analysis at each scheduled visit using the primary analysis method, the same imputation rule for the primary analysis will be used. The imputed value for missing Day 1 measures from postbaseline assessments as described in the primary analysis will not be used in the change from Day 1 analysis.

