6.13.1.2. Analysis of Diary Data

The effect of baricitinib compared to placebo up to Week 12 with regard to patient-reported outcomes (PROs) will be evaluated by the following measures:

- Duration of morning joint stiffness**

Duration of morning joint stiffness is a patient-administered item that allows for the patients to enter the length of time in minutes that their morning joint stiffness lasted each day (using a paper diary) through Visit 7 (Week 12). Duration of morning stiffness will be recorded in minutes. Durations recorded as longer than 12 hours (720 minutes) will be truncated to 720 minutes for analysis.

A nonparametric method involving the Hodges-Lehmann estimator will be used to test the treatment difference in the average durations (of morning joint stiffness) collected in the 7 days prior to Week 12. For the comparison between the baricitinib group and the placebo group, the median score and its 95% CI from the Hodges-Lehmann estimator will be presented. The p-value for the median difference will be calculated using the Wilcoxon rank-sum test. A 95% CI for the median score within each treatment group will be calculated using distribution-free confidence limits. Missing data will be handled as described for the main analysis in Section 6.13.1.1. This analysis of duration of morning joint stiffness will be

conducted using the mITT population. The PP population results will be used as supportive evidence to the mITT results. The primary analysis of duration of morning joint stiffness will also be repeated for each scheduled visit using the mITT population.

In addition, the average change of duration (of morning joint stiffness) from Day 1 across the 7 days prior to Week 12 on diary will be compared between the baricitinib group and the placebo group using the same analysis method described. The imputed value for missing Day 1 durations from postbaseline assessments as described in Section 6.13.1.1 will not be used in the change from Day 1 analysis.

- **Severity of morning joint stiffness NRS**

Severity of morning joint stiffness NRS is a patient-administered, single-item, 11-point horizontal scale anchored at 0 and 10, with 0 representing “no joint stiffness” and 10 representing “joint stiffness as bad as you can imagine.” Patients rate their morning joint stiffness each day (using a paper diary) up to Visit 7 (Week 12) by selecting 1 number that describes their overall level of joint stiffness at the time they wake up.

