An ANCOVA model will be used to test for treatment differences in the severity of morning joint stiffness NRS collected in the 7 days prior to Week 12, with treatment, country/region, and baseline joint erosion status (1-2 joint erosions plus seropositivity versus at least 3 joint erosions) as fixed effects and Day 1 value as a covariate. Missing data will be handled as described for the primary analysis in Section 6.13.1.1. Type III sums of squares for the LS means will be used for the statistical comparison; the 95% CI will also be reported. The LS mean difference, SE, CI, and p-value will be presented for the treatment difference between the baricitinib group and the placebo group. This analysis of severity of morning joint stiffness NRS will be conducted using the mITT population. The PP population results will be used as supportive evidence to the mITT results. The primary analysis of severity of morning joint stiffness NRS will also be repeated for each scheduled visit using the mITT population.

- **Tiredness severity NRS (“Worst Tiredness”)**

Worst tiredness NRS is a patient-administered, single-item, 11-point horizontal scale anchored at 0 and 10, with 0 representing “no tiredness” and 10 representing “as bad as you can imagine.” Patients rate their tiredness each day (using a paper diary) through Visit 7 (Week 12) by selecting the 1 number that describes their worst level of tiredness during the past 24 hours.

The primary analysis of “Worst tiredness” will be analyzed in a similar manner as described for severity of morning joint stiffness NRS. This primary analysis of “Worst tiredness” will be conducted using the mITT population. The PP population results will be used as supportive evidence to the mITT results. The primary analysis of “Worst tiredness” will also be repeated for each scheduled visit using the mITT population.

- **Pain severity NRS (“Worst Joint Pain”)**

Worst Joint Pain NRS is a patient-administered, single-item, 11-point horizontal scale anchored at 0 and 10, with 0 representing “no pain” and 10 representing “pain as bad as you can imagine.” Patients rate their joint pain each day (using a paper diary) through Visit 7

(Week 12) by selecting the 1 number that describes their worst level of joint pain during the past 24 hours.

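### A missing Day 1 diary score is filled with a post-randomisation score that then serves as the ANCOVA covariate for three secondary endpoints, pulling their estimates toward no effect, probably by little

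*SAP*

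**What the plan says.** SAP section 6.13.1.1 sets the missing-data rules for the diary. If Day 1 cannot be obtained, "the first available postbaseline score will be used to impute the Day 1 score", so that the patient stays in the analysis. The same imputation applies to the analyses at the earlier scheduled visits. One restriction is stated: the imputed value "will not be used in the change from Day 1 analysis".

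SAP section 6.13.1.2 models stiffness severity by ANCOVA with treatment, country/region and joint erosion status "as fixed effects and Day 1 value as a covariate", and refers back to 6.13.1.1 for missing data. Worst Tiredness and Worst Joint Pain each "will be analyzed in a similar manner as described for severity of morning joint stiffness NRS". Stiffness duration is handled differently: "The p-value for the median difference will be calculated using the Wilcoxon rank-sum test", with no covariate.

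Elsewhere, SAP section 6.1.1 defines the efficacy baseline as the "last non-missing measurement on or prior to the date of first study drug administration". Its one exception for a late value is the Physician's Global Assessment. Protocol section 12.2.7 names the Day 1 diary score as the covariate, gives no rule for a missing one and refers to the SAP.

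**The concern.** A baseline covariate is useful because randomisation balances it and treatment cannot have changed it. A postbaseline score lacks the second property. If baricitinib has begun to act when that score is written, the covariate carries part of the treatment difference, and the model subtracts the slope times that part from the estimate. The restriction in 6.13.1.1 covers only the change-from-Day-1 analysis, so the imputed value stays in the main model. That also departs from the SAP's own baseline definition. At stake are the estimates for three of the seven secondary endpoints.

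**Working it through.** **The plan's own figure.** The only power statement (SAP section 5.2) is for ACR20: 144 per arm, 60% versus 35%, two-sided 0.05. This reproduces at 0.991 against the stated 99%. It says nothing about the diary endpoints, for which no effect, SD or power is given.

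**Inputs.** From the documents: 144 per arm, 1:1 allocation, and the imputation rule and models above. Assumed, because the documents are silent:
- *m*, the share of patients with an imputed Day 1 score: 2% to 20% (20% of 288 is about 58 patients)
- *f*, the share of the Week 12 effect already present in the score used: 0 to 1, in the same direction as the Week 12 effect
- *b*, the covariate slope: about 0.5
- for the simulation: SD 2.2; true difference *d* = −1.0; correlations of 0.5 (Day 1 with Week 12), 0.8 (first postbaseline score with Day 1) and 0.65 (first postbaseline score with Week 12)

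**Formula.** The ANCOVA estimate is the difference in outcome means minus *b* times the difference in covariate means. With true Day 1 scores the second difference is zero on average. Under the SAP rule it is *m × f × d*. So the estimate is *d*(1 − *b m f*), and the proportional loss is *b × m × f*. Example: 0.5 × 0.10 × 1 = 5%.

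**Check by simulation** (3,000 trials per cell). Percentage loss, with the formula value in brackets:

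| *m* | *f* = 0.1 | *f* = 0.25 | *f* = 0.5 | *f* = 1 |
|---|---|---|---|---|
| 2% | 0.10 (0.10) | 0.26 (0.25) | 0.50 (0.50) | 1.00 (1.00) |
| 5% | 0.24 (0.25) | 0.62 (0.625) | 1.24 (1.25) | 2.58 (2.50) |
| 10% | 0.49 (0.50) | 1.29 (1.25) | 2.61 (2.50) | 5.07 (5.00) |
| 20% | 0.95 (1.00) | 2.65 (2.50) | 5.30 (5.00) | 10.48 (10.00) |

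At *f* = 0 the loss is zero within simulation error.

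**Scale.** Under these assumptions the standard error is 2.2 × √(1 − 0.5²) × √(2/144) = 0.22. A 5% loss on a 1.0-point effect is 0.05 points, about 0.2 of a standard error.

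**Error rates.** With no effect at either time point, *m* = 20%, rejection is 0.053 under the rule and 0.054 with the true Day 1 score. With a true difference of −0.6, *m* = 20% and *f* = 0.5, the estimate moves from −0.600 to −0.569 and power from 0.759 to 0.736.

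**Alternative.** Filling the missing covariate with the pooled observed Day 1 mean keeps bias within 0.2% in every cell. It does not restore power: in the last scenario power is 0.728, because a constant carries no information about the individual patient. The gain is an unbiased estimate.

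**The case against.** **The rule may be narrower.** The sentence sits in the paragraph on discontinuations, just after the provision that carries Day 1 forward for patients with no 7-day window of four scores. It could cover only them. The SAP's later references to imputed Day 1 values are general and favour the broad reading, but the text is ambiguous. The narrow reading does not rescue the rule. Few patients would be affected, but each would have the same postbaseline value as covariate and endpoint. Patients missing Day 1 but with a usable window would have no rule at all.

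**The size may be negligible.** This stands. The diary is daily, so the first available score would often be Day 2. The protocol's only onset evidence (section 7.2) is ACR20 response seen as early as 2 weeks. The upper figures need both many missing Day 1 scores and a late first score, and nothing in the documents points to either.

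**The bias is conservative.** Also true. A reader might infer that the diary results could be falsely positive, or that all four diary endpoints are compromised. Neither follows.

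**Does the SAP admit the problem?** A reader might take the bar on change from Day 1 as recognition of it. The SAP gives no reason for the bar, and a postbaseline value simply cannot define change from Day 1. The only such analysis spelled out is for stiffness duration, which has no covariate.

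**Day 1 is not strictly pre-dose either.** Protocol section 10.2 says "Items being measured using a paper diary should be completed at the end of the" patient's day, and the first dose is taken in clinic at Visit 2. So an observed Day 1 score can follow that dose by some hours. It still falls on the date of first dose, which the SAP's baseline definition allows. A later score does not.

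**Conclusion.** The point holds as a minor flaw in three secondary analyses. A post-randomisation score can enter the main ANCOVA as baseline, against the SAP's own definition, and the resulting bias is toward no effect. Its size is about slope × share imputed × share of effect present: near 0% in the most ordinary case, about 5% at 10% missing and about 10% at 20% missing if the full effect is already in the score. All of this assumes a slope of 0.5 and missing rates and early effects that the documents do not state. The documents do not support calling the diary endpoints unreliable. They do support removing the rule, since an alternative keeps every patient in the model without this bias.

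**What to change.** Change the Day 1 sentence in SAP section 6.13.1.1:
- For the covariate only, replace a missing Day 1 score with the observed Day 1 mean pooled over both arms. For Worst Tiredness and Worst Joint Pain the Visit 2 tablet score is an option: Attachment 1 of the protocol states that "Morning joint stiffness duration, Worst Tiredness, and Worst Joint Pain assessments will be collected using an electronic patient-reported outcomes" tablet at each visit. Stiffness severity is not on the tablet, so it needs the pooled mean.
- Do not use a postbaseline score as the covariate.
- For patients with neither a 7-day window of four scores nor a Day 1 score, keep the available postbaseline score as the endpoint value only.
- State which patients the rule covers, and report by arm how many have an imputed Day 1 score.

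The cost is a few lines of SAP wording and one count in the report. No new data are needed, and because SAP section 7 plans a single unblinding after final lock, the change can be made blind. Downsides: the tablet differs slightly in mode from the diary, and the pooled mean gives up a little precision.

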6.13.1.2. Analysis of Diary Data

The effect of baricitinib compared to placebo up to Week 12 with regard to patient-reported outcomes (PROs) will be evaluated by the following measures:

- Duration of morning joint stiffness**

Duration of morning joint stiffness is a patient-administered item that allows for the patients to enter the length of time in minutes that their morning joint stiffness lasted each day (using a paper diary) through Visit 7 (Week 12). Duration of morning stiffness will be recorded in minutes. Durations recorded as longer than 12 hours (720 minutes) will be truncated to 720 minutes for analysis.

A nonparametric method involving the Hodges-Lehmann estimator will be used to test the treatment difference in the average durations (of morning joint stiffness) collected in the 7 days prior to Week 12. For the comparison between the baricitinib group and the placebo group, the median score and its 95% CI from the Hodges-Lehmann estimator will be presented. The p-value for the median difference will be calculated using the Wilcoxon rank-sum test. A 95% CI for the median score within each treatment group will be calculated using distribution-free confidence limits. Missing data will be handled as described for the main analysis in Section 6.13.1.1. This analysis of duration of morning joint stiffness will be

conducted using the mITT population. The PP population results will be used as supportive evidence to the mITT results. The primary analysis of duration of morning joint stiffness will also be repeated for each scheduled visit using the mITT population.

In addition, the average change of duration (of morning joint stiffness) from Day 1 across the 7 days prior to Week 12 on diary will be compared between the baricitinib group and the placebo group using the same analysis method described. The imputed value for missing Day 1 durations from postbaseline assessments as described in Section 6.13.1.1 will not be used in the change from Day 1 analysis.

- **Severity of morning joint stiffness NRS**

Severity of morning joint stiffness NRS is a patient-administered, single-item, 11-point horizontal scale anchored at 0 and 10, with 0 representing “no joint stiffness” and 10 representing “joint stiffness as bad as you can imagine.” Patients rate their morning joint stiffness each day (using a paper diary) up to Visit 7 (Week 12) by selecting 1 number that describes their overall level of joint stiffness at the time they wake up.

An ANCOVA model will be used to test for treatment differences in the severity of morning joint stiffness NRS collected in the 7 days prior to Week 12, with treatment, country/region, and baseline joint erosion status (1-2 joint erosions plus seropositivity versus at least 3 joint erosions) as fixed effects and Day 1 value as a covariate. Missing data will be handled as described for the primary analysis in Section 6.13.1.1. Type III sums of squares for the LS means will be used for the statistical comparison; the 95% CI will also be reported. The LS mean difference, SE, CI, and p-value will be presented for the treatment difference between the baricitinib group and the placebo group. This analysis of severity of morning joint stiffness NRS will be conducted using the mITT population. The PP population results will be used as supportive evidence to the mITT results. The primary analysis of severity of morning joint stiffness NRS will also be repeated for each scheduled visit using the mITT population.

- **Tiredness severity NRS (“Worst Tiredness”)**

Worst tiredness NRS is a patient-administered, single-item, 11-point horizontal scale anchored at 0 and 10, with 0 representing “no tiredness” and 10 representing “as bad as you can imagine.” Patients rate their tiredness each day (using a paper diary) through Visit 7 (Week 12) by selecting the 1 number that describes their worst level of tiredness during the past 24 hours.

The primary analysis of “Worst tiredness” will be analyzed in a similar manner as described for severity of morning joint stiffness NRS. This primary analysis of “Worst tiredness” will be conducted using the mITT population. The PP population results will be used as supportive evidence to the mITT results. The primary analysis of “Worst tiredness” will also be repeated for each scheduled visit using the mITT population.

- **Pain severity NRS (“Worst Joint Pain”)**

Worst Joint Pain NRS is a patient-administered, single-item, 11-point horizontal scale anchored at 0 and 10, with 0 representing “no pain” and 10 representing “pain as bad as you can imagine.” Patients rate their joint pain each day (using a paper diary) through Visit 7

(Week 12) by selecting the 1 number that describes their worst level of joint pain during the past 24 hours.

The primary analysis of “Worst joint pain” will be analyzed in a similar manner as described for severity of morning joint stiffness NRS. This primary analysis of “Worst joint pain” will be conducted using the mITT population. The PP population results will be used as supportive evidence to the mITT results

- **Recurrence of joint stiffness during the day**

Recurrence of joint stiffness throughout the day is a patient-administered single-item question assessed each day (using a paper diary) through Visit 7 (Week 12) that asks “Did you have any joint stiffness throughout today, other than when you woke up?” (Yes/No).

Recurrence of stiffness during the day will be summarized as a percentage of days with the event at weekly intervals (as defined in Section 6.13.1.1) up to Visit 7 (Week 12).

Percentage of days will be analyzed by week using analysis of variance (ANOVA) with country/region, treatment group, and joint erosion status value in the model. Missing data imputation will follow what was described for the supportive analysis in Section 6.13.1.1.

